5.5. Criteria for Temporarily Delaying Administration of Study Vaccination

The following events constitute a temporary contraindication to study vaccination:

- Clinically significant pregnancy-related conditions according to medical judgement (see Section 7.2).
- Clinically significant acute illness at the time of vaccination. This does not include minor illnesses, such as diarrhea or mild upper respiratory tract infection.
- Fever (body temperature $\geq 38.0^{\circ}\text{C}$ [100.4°F]) within 24 hours prior to the planned time of vaccination.

If either of these events occur at the scheduled time for vaccination, then vaccination at a later date within the screening window is permitted at the discretion of the investigator and after consultation with the sponsor. If the vaccination cannot occur within the screening window, rescreening is required. All participants may be rescreened once (see Section 5.4).

The events listed above also apply to the booster vaccination visit for eligible participants. In addition, a urine pregnancy test (for participants of childbearing potential, according to the local guidelines) will be required for the Booster Visit for all participants in Group 4. Participants from Group 4 who are pregnant are not eligible to receive the booster vaccination (see Section 6.2).

If the vaccination visit cannot be rescheduled within the allowed window or the contraindications to vaccination persist, the rationale should be documented.

6. STUDY VACCINATION AND CONCOMITANT THERAPY

6.1. Study Vaccinations Administered

Study Vaccine Information

Ad26.COV2.S will be supplied at a concentration of 1×10^{11} vp/mL, in single-use vials, with an extractable volume of 0.5 mL. Formulation buffer will be supplied as diluent as 15 mM citrate, 5% (w/w) hydroxypropyl- β -cyclodextrin, 0.4% (w/w) ethanol, 0.03% (w/w) polysorbate 80, 75 mM NaCl, pH 6.2,

The vaccine will be extracted from the vial as outlined below:

- Ad26.COV2.S:

5×10^{10} vp dose level: 0.5 mL is withdrawn from one vial containing 0.75 mL 1×10^{11} vp/mL.

There will be no active vaccination with Ad26.COV2.S of neonates/infants in this study.

Participants will receive a single dose of Ad26.COV2.S at the 5×10^{10} vp dose level, irrespective of gestational age.

The study vaccine will be administered by IM injection into the deltoid muscle, preferably of the non-dominant arm. Subsequent booster vaccination (for Group 4 participants) are preferably administered in the opposite arm. If an injection cannot be given in the deltoid muscle due to a medical or other contraindication (for example, tattooed upper arms rendering it difficult to assess site reactogenicity), alternative locations such as the hip, thigh or buttocks can be used. If alternative locations are used for vaccine administration, the participant's ability to assess injection site events should be considered.

For information on vaccination windows, see Section 8: Study Assessments and Procedures. If a participant cannot be vaccinated within the allowed window (eg, if the window is missed due to a study pause, see Section 6.9), the decision regarding vaccination will be assessed on a case-by-case basis.

Study vaccine administration must be captured in the source documents and eCRF.

Ad26.COV2.S will be manufactured and provided under the responsibility of the sponsor. Refer to the IB ([IB 2021](#)) and its addenda for a list of excipients.

Refer to the study site investigational product and procedures manual (SIPPM) and the Investigational Product Preparation Instructions (IPPI) for additional guidance on study vaccine administration.

6.2. Booster Vaccination

Vaccine Naïve Participants

Vaccine naïve participants at study entry (Group 4, including Sentinel and Safety Cohorts) who have completed the pregnancy during which they were enrolled in the study, are not pregnant again will be offered an (optional) booster vaccination with a single dose of Ad26.COV2.S at 5×10^{10} vp. They must not meet any study discontinuation criteria as specified in Section 7.1 and have not received another COVID-19 vaccine (eg, national immunization program) outside the study as indicated in the SoA in Section 1.3.1.1.

The booster vaccination will be administered not earlier than 2 months after completion of the participant's Ad26.COV2.S vaccination in the study. The booster vaccination and the booster follow-up visit should not extend the study duration.

The Booster Vaccination Visit for vaccine naïve participants at study entry should preferably coincide with a scheduled visit from the original SoA in Section 1.3.1. If not operationally feasible to coincide with an existing visit, an unscheduled visit may be planned.

Participants will continue to follow the Schedule of Activities in Section 1.3.1. All participants (whether they consent to the booster vaccination or not) will be encouraged to remain in the study.

Previously Vaccinated Participants (Group 1-3)

Previously vaccinated participants (Groups 1-3) will receive a single (booster) dose of Ad26.COV2.S at 5×10^{10} vp as part of the study, but are not eligible for a second booster during the study.

6.3. Preparation/Handling/Storage/Accountability

Preparation/Handling/Storage

All study vaccine must be stored in a secured location with no access for unauthorized personnel and at controlled temperatures as indicated on the clinical labels. If study vaccine is exposed to temperatures outside the specified temperature range, all relevant data will be sent to the sponsor to determine if the affected supplies can be used or will be replaced. The affected study vaccine must be quarantined and not used until further instruction from the sponsor is received.

Refer to the SIPPM and the IPPI for additional guidance on study vaccine preparation, handling, and storage.

A pharmacist or other qualified individual will prepare the appropriate vial and syringe, labeled with the participant's identification number, and provide the syringe to the vaccine administrator (a trained and qualified study nurse, medical doctor, otherwise qualified HCP) who will perform the injection.

Accountability

The investigator is responsible for ensuring that all study vaccine received at the site is inventoried and accounted for throughout the study. The study vaccine administered to the participant must be documented on the vaccine accountability form. All study vaccine will be stored and disposed of according to the sponsor's instructions. Study site personnel must not combine contents of the study vaccine containers.

Study vaccine must be handled in strict accordance with the protocol and the container label and must be stored at the study site in a limited-access area or in a locked cabinet under appropriate environmental conditions. Unused study vaccine must be available for verification by the sponsor's study site monitor during on-site monitoring visits. The return to the sponsor of unused study vaccine will be documented on the vaccine accountability form. When the study site has an authorized destruction unit and study vaccine supplies are destroyed on-site, this must also be documented on the vaccine accountability form.

Potentially hazardous materials containing hazardous liquids, should be disposed of immediately in a safe manner and therefore will not be retained for vaccine accountability purposes.

Study vaccine should be dispensed under the supervision of the investigator or a qualified member of the study site personnel, or by a hospital/clinic pharmacist. Study vaccine will be administered only to participants participating in the study. Returned study vaccine must not be dispensed again, even to the same participant. Study vaccine may not be relabeled or reassigned for use by other participants. The investigator agrees neither to dispense the study vaccine from, nor store it at, any site other than the study sites agreed upon with the sponsor. Further guidance and information for the final disposition of unused study vaccine are provided in the SIPPM.

Measures to Minimize Bias: Vaccine Allocation

Sentinel and Safety Cohorts participants received 1 dose of Ad26.COV2.S at 5×10^{10} vp. At the time of writing Amendment 5, the IDMC confirmed that the safety profile of 1 dose of Ad26.COV2.S at 5×10^{10} vp was considered acceptable and no safety concerns were identified following review of the Sentinel and Safety Cohorts safety data. The remaining participants will receive 1 dose of Ad26.COV2.S at 5×10^{10} vp.

Participants will be stratified by pregnancy stage (Weeks ≥ 16 to < 28 or Weeks ≥ 28 to ≤ 38). Efforts will be made to enroll at least approximately 25% per trimester, per group. The assignment will utilize a computer-generated schedule prepared before the study under the sponsor's oversight.

Participants who were vaccine naïve at study entry will be offered a booster dose of Ad26.COV2.S at 5×10^{10} vp during the study.

Blinding

This is an open-label study, therefore, blinding procedures are not applicable.

6.4. Study Vaccination Compliance

Study vaccines will be administered IM by qualified study site personnel at the study site per local regulations. Details of each administration will be recorded in the eCRF (including date and time of injection, and the location used for injection [deltoid or alternative location]).

6.5. Dose Modification

The safety and tolerability of a single dose of the Ad26.COVS vaccine at 5×10^{10} vp in adult participants was assessed in Sentinel and Safety Cohorts.

At the time of writing Amendment 5, the IDMC confirmed that the safety profile of 1 dose of Ad26.COVS at 5×10^{10} vp was considered acceptable and no safety concerns were identified following review of the Sentinel and Safety Cohorts safety data.

The remaining participants will receive 1 dose of Ad26.COVS at 5×10^{10} vp dose level.

6.6. Continued Access to Study Vaccine After the End of the Study

Not applicable.

6.7. Treatment of Overdose

For this study, any dose of Ad26.COVS greater than the assigned dose will be considered an overdose. The sponsor does not recommend specific treatment for an overdose.

In the event of an overdose, the investigator should:

- Contact the relevant sponsor or delegate immediately.
- Closely monitor the participant for AEs/SAEs/pregnancy-related AEs/MAAEs (ie, the participant will remain at the study site for at least 1 hour and will be closely monitored for allergic or other reaction by study staff. Follow-up telephone calls 12 hours and 24 hours post-vaccination can be made).
- Document the quantity of the excess dose in the eCRF.
- Report as a special reporting situation.

6.8. Prestudy and Concomitant Therapy

Prestudy therapies such as analgesic/antipyretic medications and non-steroidal anti-inflammatory drugs, corticosteroids, and antihistamines used 30 days before administering the study vaccine must be recorded.

Concomitant therapies such as analgesic/antipyretic medications and non-steroidal anti-inflammatory drugs, corticosteroids, antihistamines, and vaccinations must be recorded (including dose and frequency) from study vaccination until 28 days after administration of study vaccine. All other concomitant therapies should also be recorded if administered in conjunction with a confirmed COVID-19 case or with new or worsening AEs or suspected AESI reported per protocol requirements outlined in Section 8.3.1.

Concomitant therapies associated with an SAE meeting the criteria outlined in Section 10.4.1 will be collected and recorded in the eCRF from study vaccination through the end of the study for adult participants and from birth until the end of the study for neonates/infants. Concomitant therapies associated with MAAEs will be collected and recorded in the eCRF from study vaccination until 6 months after vaccination for adults and from birth until 6 months of age for neonates/infants. Concomitant therapies associated with AEs leading to study discontinuation will be recorded in the eCRF during the entire study for both adult and neonates/infants.

Use of any investigational medication (including experimental vaccines other than the study vaccine) during the study, other than the study vaccine, will lead to discontinuation of administration of any subsequent study vaccination. Participants may not receive:

- an investigational drug or use an invasive investigational medical device within 30 days, or
- investigational immunoglobulin or monoclonal antibodies within 3 months, or
- convalescent serum for COVID-19 treatment within 4 months, or
- an investigational vaccine (including investigational Adenoviral-vectored vaccines) within 4 months before the planned administration of study vaccine.

During the study, the use of investigational COVID-19 vaccines other than the study vaccine is not allowed, and the use of investigational drugs is only allowed if medically indicated. In the event that a participant receives another COVID-19 vaccine outside of the study, investigators are required to enter any COVID-19 vaccines (name/manufacturer of the vaccine and date of administration) in the Concomitant Therapy eCRF.

Treatment with investigational COVID-19 drugs after diagnosis of a COVID-19 case is allowed during the postpartum follow-up period and needs to be recorded in the COVID-19 episode description.

Licensed live attenuated vaccines are generally contraindicated during pregnancy. Licensed (not live) vaccines (eg, the DtaP [reduced Diphtheria toxoid, Tetanus toxoid, and acellular Pertussis], influenza, tetanus, hepatitis A, hepatitis B, rabies vaccines) should be given at least 14 days before or at least 14 days after administration of study vaccine in order to avoid potential confusion of adverse reactions and potential immune interference, and must be recorded. The use of any coronavirus vaccine (licensed or investigational) is disallowed at any time prior to vaccination except for those licensed vaccines indicated in inclusion criteria. The use of any coronavirus vaccine (licensed or investigational) is disallowed during the study, and must be reported in EDC. If a vaccine is indicated in a post-exposure setting (eg, rabies or tetanus), it should take priority over the study vaccine, and any vaccinations must be recorded.

All vaccines administered to the babies during the study should be captured.

Treatment with immunoglobulins and blood products is disallowed in the 3 months and 4 months before the planned administration of study vaccine, respectively, and during the study. Immunoglobulin Rho (D) can be given at any time.

Antipyretics (eg, acetaminophen/paracetamol) after vaccination, and additional doses spaced 6 hours apart may be administered thereafter for symptom relief as needed. Prophylactic antipyretic use is not encouraged; however, it could be considered per investigator's discretion.

Chronic (daily for 2 consecutive weeks) or recurrent use of systemic corticosteroids (>20 mg/day of prednisone or equivalent)^a at immunosuppressive doses and administration of antineoplastic and immunomodulating agents or radiotherapy are prohibited during the study and within 6 months before the planned administration of study vaccine. If any of these agents are indicated in a disease setting, treatment takes priority over the study vaccine.

Refer to Section 5.2 for further details of prohibited therapy.

The sponsor must be notified as soon as possible of any instances in which prohibited therapies are administered. Depending on the time of the occurrence, any participant who receives a prohibited concomitant medication will not be included in the immunogenicity analyses.

6.9. Study Vaccination Pausing Rules

The Sponsor (including designated sponsor teams) and/or Sponsor Committee as well as the Investigator(s) will monitor safety, including the study vaccination pausing rules.

If a study vaccination is considered to raise significant safety concerns (and a specific pause rule has been met), further vaccination of participants will be paused.

The IDMC will review all available safety data and make recommendations regarding the continuation of the study to the sponsor study team. The formal recommendation from IDMC will be provided by the sponsor to applicable health authorities.

The occurrence of any of the following events will lead to a pause in further study vaccination:

1. Death of an adult participant, considered related to study vaccine or if the causal relationship to the study vaccine cannot be excluded; OR
2. One or more adult participants experience an SAE, a suspected AESI or a Grade 4 (solicited or unsolicited) AE or a persistent (upon repeat testing) Grade 4 laboratory abnormality that is determined to be related to study vaccine; OR
3. Three or more adult participants experience a Grade 3 unsolicited AE of the same type (per medical judgement of the sponsor), that is determined to be related to study vaccine; OR
4. Three or more adult participants experience a persistent (upon repeat testing) Grade 3 laboratory abnormality related to the same laboratory parameter and considered related to study vaccine; OR

^a Note: Ocular, topical or inhaled steroids are allowed.

5. Three or more adult participants experience a Grade 3 solicited AE of the same type, determined to be related to study vaccine, and persisting as Grade 3 for longer than 3 consecutive days (ie, the day of occurrence of the AE is counted as Day 1).^a

For number 2 and number 4: to assess abnormal laboratory values, the test must be repeated at least once, within 48 hours of the site becoming aware of the abnormal value.

For number 2, number 3, and number 5: after each IDMC review of similar AEs, the Committee will indicate the conditions under which it requires further notification and review of any subsequent similar AEs.

Note: the occurrence of a study pause in any other ongoing study with Ad26.COV2.S may trigger a pause in further vaccination in the current study, if considered to be medically relevant. Any subsequent study visits as a result of a delayed vaccination following a study pause are not considered to be protocol violations, however, the data at these timepoints may be eliminated from certain statistical analyses.

Based on the pausing criteria, the sponsor will notify other sites in case of a study pause. To enable prompt response to a situation that could trigger pausing rules, the investigator should notify the sponsor, immediately and no later than 24 hours after becoming aware of any related AE of Grade 3 or above and update the eCRF with relevant information on the same day the AE information is collected.

A thorough analysis of all Grade 3 (or above) cases will be carried out by the sponsor, irrespective of whether the criteria for pausing the study are met. Based on the pausing criteria, the sponsor will notify other sites in case of a study pause. The sponsor's medical monitor or designee is responsible for notification of IDMC members in case a study pause is declared.

Vaccinations for an individual participant may be suspended for safety concerns other than those described in the pausing criteria, at the discretion of the investigator if he/she feels the participant's safety may be threatened. The sponsor may initiate IDMC review for any single event or combination of multiple events which, in their professional opinion, could jeopardize the safety of the participants or the reliability of the data.

Resumption of vaccinations will start upon receipt of written recommendations by the IDMC. If any pausing rule is met (refer to Section 10.3.6 Safety Monitoring Committee Structure) and, if following appropriate safety review it is deemed appropriate to restart dosing, the sponsor will comply with regulatory requirements per competent authority(ies).

The clinical site(s) will be allowed to resume activities upon receipt of a written notification from the sponsor. These communications from the IDMC will be forwarded to relevant parties according to local regulations.

^a The day of occurrence of the AE is counted as Day 1.

7. DISCONTINUATION OF STUDY VACCINATION AND PARTICIPANT DISCONTINUATION/WITHDRAWAL

7.1. Discontinuation of Study Vaccination

Study vaccinations will be withheld for the reasons listed below. These participants could remain on the study for safety and immunogenicity follow-up. Additional unscheduled visits may be performed for safety reasons, if needed. In case of questions, the investigator is encouraged to contact the sponsor.

A participant's study vaccination must be discontinued if:

- Any serious related AE, worsening of health status or intercurrent illnesses that, in the opinion of the investigator, requires discontinuation from study vaccine.
- Anaphylactic reaction following vaccination, not attributable to causes other than vaccination.
- SAE or other potentially life-threatening (Grade 4) event that is determined to be related to study vaccine.
- Chronic (daily for 2 consecutive weeks) or recurrent use of systemic corticosteroids (>20 mg/day of prednisone or equivalent)^a and administration of antineoplastic and immunomodulating agents or radiotherapy.
- Withdrawal of consent to receive further study vaccination.
- Participant receives a experimental medication (including vaccines during the study) or receives a COVID-19 vaccine outside the study.
- Participant who had previously experienced TTS or HIT.
- Participant who has previously experienced CLS or GBS.

7.2. Delay or Discontinuation of Vaccination due to Pregnancy-Specific Complications

The booster vaccination (Group 4 only) (see Section 6.2) may be withheld or delayed if the participant experiences any of the following pregnancy-specific complications prior to the scheduled booster vaccination:

- severe vaginal bleeding;
- preterm premature rupture of membranes;
- severe pre-eclampsia, eclampsia;
- hemolysis elevated liver enzymes and low platelets (HELLP) syndrome;
- stillbirth;
- fetal loss;

^a Note: Ocular, topical or inhaled steroids are allowed.

- preterm birth;
- participant has a positive diagnostic molecular test result for SARS-CoV-2 infection on the day of the booster vaccination.

In the event that any of the above occurs, the participant (and infant, if applicable) will continue to be followed until the end of the study in accordance with the [Schedules of Activities](#).

7.3. Participant Discontinuation/Withdrawal From the Study

A participant will be withdrawn from the study for any of the following reasons:

- Lost to follow-up
- Withdrawal of consent
- Death
- Repeated failure to comply with protocol requirements

When a participant withdraws before study completion, the reason for withdrawal is to be documented in the eCRF and in the source document. If the reason for withdrawal from the study is withdrawal of consent, then no additional assessments are allowed.

For those participants who are unable to continue participation in the study up to the last planned study visit, but for whom consent is not withdrawn, an early exit visit will be conducted as soon as possible. Participants who wish to withdraw consent from participation in the study will be offered an optional visit for safety follow-up. This includes the safety assessments of the early exit visit (no blood sampling for immunogenicity).

Withdrawal of Consent

A participant declining to return for scheduled visits does not necessarily constitute withdrawal of consent. Alternate follow-up mechanisms that the participant agreed to when signing the consent form apply as local regulations permit.

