- d. Participant should be encouraged by the site to have nasal swabs collected as indicated in the Schedule of Activities. If the participant is unable or unwilling to have all samples collected as requested, the participant should still complete the other COVID 19 assessments, including the visit at COVID 19 Day 29.
- e. If the nasal swabs collected on COVID 19 Day 1 2 and COVID 19 Day 3 5 are negative for SARS CoV 2, the participant will not undertake any further COVID 19 procedures and will fall back to the default Schedule of Activities in Section 1.3.1 or Section 1.3.2 until the end of the study/early withdrawal.

- f. Participants should undertake the COVID 19 procedures until 14 days after symptom onset (COVID 19 Day 15) or until resolution of the COVID 19 episode, whichever comes last. Resolution of a COVID 19 episode is defined as having 2 consecutive SARS CoV 2 negative nasal swabs and 2 consecutive days with no COVID 19 related signs or symptoms. Once past COVID 19 Day 15, participants should stop the collection of nasal swabs samples as soon as 2 consecutive nasal samples are SARS CoV 2 negative, but (if still symptomatic at that time) should continue completing the ePROs (including SIC, body temperature, and pulse oximetry) in the eCOA until 2 consecutive days with no COVID 19 related signs or symptoms.
- g. Only applicable for participants that have at least 1 SARS CoV 2 positive nasal swab collected on COVID 19 Day 1 2 or Day 3 5. COVID 19 Day 29 should still be performed even if the nasal swab results are still pending.
- h. The visit on COVID 19 Day 29 can be combined with a regular study visit if within the applicable visit windows.
- i. The COVID 19 Day 1 2 nasal swab can be collected at the study site (or hospital or other location, if needed), if preferred by the participant.
- j. All COVID 19 Day 3 5 and Day 29 assessments may be performed by a trained HCP at the participant's home, if allowed per local regulations.
- k. If a participant has a positive test result for SARS CoV 2 infection and/or depending on the medical status of the participant. If necessary, study site personnel or a trained HCP may visit the participant at home (or at the hospital or other location, if needed), if allowed by local regulations. Under these circumstances, the participant will be contacted by the site at least once per week.

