For vaccine naïve participants at study entry who receive a booster vaccination, blood samples will be collected from adults pre-boost and 28 days post-boost for humoral immunogenicity assessments and whole blood will be collected for the analysis of vaccination-related biomarkers.

Further details about the immunogenicity assessments are provided in Section 8.1.1.

Active surveillance for COVID-19-like signs and symptoms in participants and neonates/infants will occur, including a COVID-19 surveillance (symptom check) through the participant's electronic diary eCOA.

For the duration of the study, each participant or parent(s)/caregiver(s) for the neonate/infant will be asked at least twice a week, through the eCOA, if the participant or their neonate/infant have experienced any new symptoms or health concerns that could be related to infection with SARS-CoV-2 ([suspected] COVID-19 surveillance [symptom check]).

All participants and neonates/infants with COVID-19-like signs or symptoms and all participants and neonates/infants with a positive RT-PCR test from outside the study meeting the prespecified criteria for suspected COVID-19 should undertake prespecified COVID-19 procedures as outlined in the Schedule of Activities in Section 1.3.4 and Section 1.3.5, respectively.

If neonates were born to mothers with confirmed COVID-19, or if a close relative from the same household as the neonate/infant has confirmed COVID-19, testing for SARS-CoV-2 should be performed for the neonate/infant, regardless of whether there are signs of infection in the neonate/infant. Details are provided in Section 8.1.2. The occurrence of asymptomatic SARS-CoV-2 infection will also be assessed, if feasible (see Section 8.1.4).

Site staff and participants will not be blinded as to the outcome of the molecular test results from the local (hospital) laboratory. Their routine HCP can obtain external diagnostics, including RT-PCR or other molecularly confirmed viral tests, as medically needed.

All necessary precautions (per local regulations) should be taken to protect site staff and other contacts of participants and neonates/infants who are confirmed to have COVID-19 until proven negative by molecular techniques or until resolution.

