5.3. Lifestyle Considerations

Potential adult participants must be willing and able to adhere to the following lifestyle restrictions during the course of the study to be eligible for participation:

1. Refer to Section 6.8 for details regarding prohibited and restricted therapy during the study.
2. Agree to follow all requirements that must be met during the study as noted in the Inclusion and Exclusion Criteria for adult participants (Section 5.1 and Section 5.2).
3. Adult participants should agree to follow requirements for the electronic completion of the COVID-19 signs and symptoms surveillance questions in the eCOA, as applies to both themselves and to their neonate/infants.

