The site staff will be provided with ePRO and ObsRO completion guidelines that includes instructions on capturing responses in the eCOA and grading scales to assess severity of the signs and symptoms after vaccination (reactogenicity). The study staff is responsible for providing appropriate training to the participant/parent(s)/caregiver(s) to prevent missing or incorrect data. The reactogenicity diary will be reviewed by the study personnel at the Day 8 visits indicated in the Schedule of Activities (Section 1.3.2 and Section 1.3.3, respectively). If the reactogenicity diary review is missed/unavailable at Day 8, the reactogenicity diary will be reviewed during the following visit.

Sites should reach out to a participant if the participant fails to complete any of the questions displayed in the eCOA. The questionnaire will be accessible on the eCOA platform in between scheduled reminders and participants will be encouraged to answer the surveillance question in the eCOA as soon as possible after the onset of COVID-19-like symptoms, or any other symptoms with new onset, including those listed above. Every effort will be made to document the status of all participants that are lost to follow-up due to not completing the eCOA and for whom hospitalization has not been recorded.

If multiple assessments are scheduled for the same timepoint, it is recommended that procedures be performed in the following sequence: (a) for adult participant: physical/obstetric examination and vital signs, ultrasound blood draws, and vaccination; (b) for neonate/infant: physical examination and vital signs, blood draws. If needed, assessments may be performed at another day within the applicable visit window. Actual dates and times of assessments will be recorded in the source documentation and eCRF.

Adult participants will also be provided with a kit to collect nasal swabs at Day 1 to be used in case they experience COVID-19-like symptoms during the study (see Section 8.1.2). In the event of the neonate/infants developing COVID-19 like symptoms, the parent(s)/caregiver(s) should contact the site, who will provide a trained HCP to collect nasal swabs from the neonate/infant.

If allowed by local regulations, study visits other than screening and vaccination visit may take place at other locations if there are travel restrictions in case of exceptional situations (eg, pandemic).

Blood Collection - Adult Participants

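### Section 7.3 requires study withdrawal for undefined repeated non-compliance without withdrawal of consent, and states no outcome or safety collection beyond one early exit visit

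*Protocol*

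**What the plan says.** Section 7.3 opens its list with "A participant will be withdrawn from the study for any of the following reasons". The reasons are loss to follow-up, withdrawal of consent, death, and "Repeated failure to comply with protocol requirements". No threshold is given for what counts as repeated, and no list of which requirements count.

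For participants who cannot continue but "for whom consent is not withdrawn, an early exit visit will be conducted as soon as possible". The bar on anything further is confined to one reason: "If the reason for withdrawal from the study is withdrawal of consent, then no additional assessments are allowed".

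Completing the eCOA is a protocol requirement. Section 5.3 says "Adult participants should agree to follow requirements for the electronic completion of the COVID-19 signs and symptoms surveillance questions in the eCOA", for the woman and her infant. Section 4.1 says each participant or caregiver "will be asked at least twice a week, through the eCOA, if the participant or their neonate/infant have experienced any new symptoms", for the duration of the study.

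Section 3 sets the primary SAE and AESI endpoint from vaccination to at least 12 months after delivery. Pregnancy outcomes, and infant safety and outcomes to about 12 months of age, are secondary endpoints.

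**The concern.** Non-compliance is normally a reason to leave someone out of a per-protocol analysis, not to stop observing her. Here it is a mandatory reason to leave the study, alongside death and withdrawal of consent. A woman who keeps missing her symptom checks, but who is reachable and content to be followed, can fall under the bullet as worded.

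If she is removed before delivery, her pregnancy outcome is at stake. If she is removed afterwards, her new SAEs and AESIs to 12 months postpartum are. Enrolment ceased with Amendment 7, so she cannot be replaced. Adherence may fall when a woman is ill, the pregnancy is complicated or the infant is sick, so those removed may not resemble those who stay. Because the term is undefined, sites may also apply it differently.

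**Working it through.** **What follows withdrawal, provision by provision**

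- Section 7.3: one early exit visit if consent is not withdrawn. Nothing is scheduled after it.
- Schedules 1.3.1 and 1.3.2: the early exit visit records adverse maternal and fetal outcomes and AEs, SAEs, AESIs and MAAEs up to that point. Section 8.2.1 provides for an obstetric examination if the woman is still pregnant at early exit, so exit before delivery is foreseen. No text then requires the outcome of that pregnancy to be obtained.
- Section 8.3.1: adult SAE and AESI reporting runs to the participant's last study-related procedure. That may include a safety contact, but none is scheduled after early exit. The section also gives a general SAE window to end of study or at least 12 months postpartum, without saying how it would be met for someone already withdrawn.
- Section 10.4.5: SAEs unresolved at discontinuation are followed. This does not cover new events or the pregnancy outcome.
- Infant: Section 7.4 treats neonates and infants as participants, and Section 1.3.3 gives them their own early exit visit. No text withdraws the infant with the mother. Equally, no text protects the infant's follow-up or exempts the infant from the Section 7.3 list.

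Compare neighbouring sections. Section 7.1 allows participants to stay for follow-up once study vaccination is discontinued, and Section 7.2 keeps mother and infant in follow-up to the end of the study. Section 7.3 has no equivalent sentence for non-compliance.

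**How many symptom checks there are to miss**

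This takes two checks a week and assumes delivery at Week 40:

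- Vaccinated at Week 16: (24 + 52) × 2 = 152 maternal checks.
- Vaccinated at Week 38: (2 + 52) × 2 = 108.
- Infant to 12 months: 52 × 2 = 104.

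**Effect on precision**

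The protocol's zero-event upper limit is the two-sided 95% exact limit, 1 − 0.025^(1/n). It reproduces Table 5: n = 25 gives 13.7%, 40 gives 8.8%, 60 gives 6.0%, 100 gives 3.6%, 120 gives 3.0% and 240 gives 1.5%.

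The final number enrolled is not stated. The sizes and losses below are therefore illustrations.

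| Assumed women | Lost | Remaining | Upper limit, no events |
|---|---|---|---|
| 40 | 0 | 40 | 8.8% |
| 40 | 2 (5%) | 38 | 9.25%, i.e. 9.3% |
| 40 | 4 (10%) | 36 | 9.7% |
| 22 (Sentinel and Safety Cohorts only) | 0 | 22 | 15.4% |
| 22 | 2 | 20 | 16.8% |
| 22 | 4 | 18 | 18.5% |

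**The case against.** The strongest reply is that the protocol's specific provisions point away from removal.

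- **Missed swabs.** A reader might infer that these lead to withdrawal. They should not: Section 1.3.4 says that a participant unable or unwilling to give all samples continues, in that "the participant should still complete the other COVID 19 assessments", and Sections 1.3.5 and 8.1.2 say the same for infants.
- **Missed eCOA entries.** Section 8 has the site contact the participant, and staff may collect answers on her behalf. No text names a missed diary as grounds for removal. This stands as the first response, but nothing says it replaces Section 7.3, and eCOA completion is a stated requirement.
- **Contradiction with Section 8.** Its sentence "Every effort will be made to document the status of all participants that are lost to follow-up due to not completing the eCOA" concerns participants lost to follow-up, a separate bullet in Section 7.3. The swab footnote governs assessments within a COVID-19 episode. Both can be obeyed alongside Section 7.3, so neither contradicts it.
- **Infant data.** That the infant leaves with the mother is an inference. The infant is a separate participant, and consent for infant follow-up is given at maternal screening.
- **Other follow-up.** Section 7.3 says that alternate follow-up agreed in the consent form applies when a participant declines visits. That sentence sits under withdrawal of consent and is not tied to withdrawal for non-compliance, but it means one cannot say that later data will certainly not be collected.
- **Size.** The numbers lost are assumed, the study is descriptive, and nothing in the protocol shows that non-compliance tracks adverse outcomes.

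These points narrow the concern. They leave a mandatory, undefined rule with no stated collection after early exit for a woman who still consents.

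**Conclusion.** The point holds in a limited form. Section 7.3 requires withdrawal for undefined repeated non-compliance while consent stands, and specifies one early exit visit. Followed as written, it leaves no stated collection of the pregnancy outcome or of new SAEs and AESIs to 12 months postpartum, and no express protection of the infant's follow-up. That works against endpoints running to at least 12 months after delivery.

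The precision cost is small: about 0.4 to 0.9 percentage points on the zero-event limit (9.25 − 8.81 and 9.74 − 8.81) with an assumed 40 women and two to four losses, and 1.4 to 3.1 points (16.84 − 15.44 and 18.53 − 15.44) with 22. Informative loss is the more important possibility, but the documents do not establish it. Nor do they support saying that safety follow-up ends altogether or that rates will be biased low. This should be corrected, mainly because it is easily avoided.

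**What to change.** Remove the non-compliance bullet from the study-withdrawal list in Section 7.3. Alternatively, limit it to study procedures and to the per-protocol immunogenicity sets, which under Section 9.3 already exclude major deviations expected to affect immunogenicity.

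Add that, unless consent is withdrawn, pregnancy outcome, maternal SAEs and AESIs, and infant safety and outcomes continue to be collected to 12 months by phone or medical records, as consent and local regulations permit. The schedules already use medical records for deliveries at hospitals where site staff lack privileges.

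The protocol edit is a few sentences. The cost is record retrieval for a few women and more missing diary data in the database. The consent form should be checked to confirm that it covers collection after early exit; if it does not, it would need a matching change.
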